2.3.1 Risk assessment

To date, efficacy and safety data from ongoing studies of tusamitamb ravtansine (TED13751, TCD15054, and EFC15858) support the continued clinical development of tusamitamb ravtansine. Based on available safety data, the main anticipated risk to patients is corneal toxicity presenting as microcystic keratopathy, which is reversible and manageable with dose delay and dose reduction in some patients. Peripheral neuropathy is an identified risk in patients previously exposed to neurotoxic drugs.

Other potential risks were observed in a limited number of patients, and clinical pictures were consistent with a presentation in patients with underlying relevant risk factors. These potential risks include colitis ([including hemorrhagic], mainly in participants with a known history of colitis or gastrointestinal tract conditions), cardiotoxicity (myocardial or conduction abnormalities), hematologic cytopenias, and hepatotoxicity, as well as systemic acute hypersensitivity reactions (including anaphylaxis; Table 1).

27-Sep-2021
Version number: 1

Table 1 - Risk assessment

Potential risk of clinical significance	Summary of data/rationale for risk	Mitigation strategy
Study intervention: tus	samitamab ravtansine	

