Microcystic keratopathy/Keratitis	 Nonclinical: Mitotic arrest/single cell necrosis in the cornea of the eye in mice and monkeys. In addition, brown discoloration of the cornea associated, microscopically, with minimal dark pigmentation in cornea epithelial cells in monkeys. Findings considered related to the cytotoxic properties of DM4. Clinical: Reversible non-inflammatory, microcystic keratopathy/keratitis. Main dose-limiting toxicity (DLT) in the dose escalation part of study TED13751. Observations in the different phases of the clinical trial showed nonserious, mild to moderate AEs, no Grade 4-5 AEs were reported. The corneal TEAEs were manageable and reversible. Corneal TEAEs appeared: In TED13751 study in 30.1% of patients (56/186) in the pool of patients at 100 mg/m² Q2W, 32.1% of patients (9/28) in the Loading dose cohort, and 40.0% of patients (6/15) in the Dose Escalation Q3W phase. In TCD15054, in 50% of patients in the main dose escalation (3/6 patients) and in 50% of patients in the loading dose (8/16 patients). Regarding the ongoing studies ACT16525, ACT16146, ACT16432, EFC15858 among the patients treated there was no serious TEAE of keratopathy/keratitis. 	Careful collection of medical history and physical examination. Assessment of ocular/visual symptoms at each visit before IMP administration. Specific ocular tests at screening, whenever clinically indicated and at EOT. Wearing of contact lenses is forbidden. Preventive instillation of artificial tears or hyaluronic ophthalmic gel drops. Curative action: dose delay and reduction; artificial tears, corticosteroid eye drops and symptomatic treatment; ophthalmologist follow-up.

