3.6.2 Adverse events

General common rules for adverse events

All AEs will be graded according to the National Cancer Institute Common Terminology for Adverse Events (NCI-CTCAE version 5.0) and coded to a lower-level term (LLT), preferred term (PT), high-level term (HLT), high-level group term (HLGT), and associated primary system organ class (SOC) using the Medical Dictionary for Regulatory Activities (MedDRA) version in effect at Sanofi at the time of database lock.

The AEs will be analyzed in the following 3 categories:

- Pre-treatment AEs: AEs that developed, worsened or became serious during the pre-treatment period.
- Treatment-emergent adverse events (TEAE)s: AEs that developed, worsened or became serious during the treatment-emergent period.
- Post-treatment AEs: AEs that developed, worsened or became serious during the post-treatment period.

Similarly, deaths will be analyzed in the pre-treatment, treatment-emergent and post-treatment periods.

The primary AE analyses will be on TEAEs. Pre-treatment and post-treatment AEs will be described separately.

An AE with incomplete or missing date/time of onset (occurrence, worsening, or becoming serious) will be classified as a TEAE unless there is definitive information to determine it is a pre-treatment or a post-treatment AE.

If the assessment of the relationship to IMP is missing for an AE, this AE will be assumed as related to IMP. Missing grade will be left as missing.

Multiple occurrences of the same event in the same participant will be counted only once in the tables within a treatment phase, using the maximum (worst) grade by treatment phase. Summaries will be provided for all grades combined and for grade ≥ 3 (including grade 5). Missing grades, if any, will be included in the "All Grades" category.

The AE tables will be sorted as indicated in Table 4.

Table 4 - Sorting of AE tables		
AE presentation	Sorting rules	
SOC, HLGT, HLT and PT	By the internationally agreed SOC order and by alphabetic order of HLGTs, HLTs and PTs.	
SOC and PT	By the internationally agreed SOC order and decreasing frequency of PTs ^{a, b}	
[SMQ/CMQ] and PT	By decreasing frequency of SMQs/CMQs and PTs ^a	
PT	By decreasing frequency of PTs ^a	

Sorting will be based on the SAR408701 group incidence. а

The table of all TEAEs presented by primary SOC and PT will define the presentation order for all other tables (eq, treatment-emergent b SAEs) presented by SOC and PT, unless otherwise specified.

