- Outcome: in case of multiple events with different outcomes, the most severe outcome will be tabulated and selected according to the following order of severity: fatal, not recovered or resolved, recovering or resolving, recovered or resolved with sequelae, recovered or resolved, unknown

In addition, analyses on occurrence and recurrence of corneal events will be provided. An occurrence of corneal event is defined as one or a group of concomitant corneal events. A recurrence is defined as any new occurrence of corneal event starting after a previous resolved occurrence.

- The number of occurrences by participant
- The time to first onset of corneal event will be described using Kaplan-Meier curves. Time to first onset is defined as the time from the date of first IMP administration to the date of the first occurrence of the event. In the absence of an event before the analysis cut-off date, it will be censored at the end date of the treatment-emergent period, analysis cut-off date or date of death, whichever occurs first.

- The time to recovery will be summarized using descriptive statistics in participants who had had at least one recovered or resolved occurrence of corneal event (with or without sequelae), considering the longest duration among all occurrences by participant.
- The time to recurrence will be summarized using descriptive statistics in participants who had had at least one recurrence, considering the shortest time among all recurrences by participant.

Besides the AE categorized as ocular/visual adverse events, all ocular/visual symptoms (coded term) recorded in e-CRF as associated symptom of the reported ocular treatment-emergent adverse events will be reported as descriptive analysis. Same analysis will be done separately for ocular/visual symptoms associated to corneal TEAEs (CMQ)."

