3.6.3.2 Ocular examinations

Schirmer test

Participants reported Schirmer's test will be classified into three classes at baseline: normal ≥ 10 mm, moderate >5 and <10 mm, severe ≤ 5 mm (8). The worst classification between the laterality will be considered. A frequency table of the baseline status with and without anaesthetics will be provided by treatment group for the participants with corneal events (CMQ) during the treatment-emergent period and for the participants without event.

Visual acuity test

Analyses are done on the best corrected visual acuity assessed using Snellen Chart method.

Frequency tables on best corrected visual acuity (BCVA) measured during on-treatment period will be performed separately on all participants and on participants who experienced at least one treatment-emergent corneal event:

- on the worst change from baseline: No worsening versus baseline, Worsening versus baseline (1 to 3 lines decrease versus baseline, or >3 lines decrease versus baseline)
- on the worst absolute value: No change versus baseline, Worsening versus baseline: BCVA equals to 20/40 or better, BCVA worse than 20/40 up to 20/200, BCVA 20/200 or worse.

- on the CTCAE worst vision decrease: No worsening versus baseline, BCVA equals to 20/40 or better or 1 to 3 lines decrease versus baseline, BCVA worse than 20/40 up to 20/200 or >3 lines decrease versus baseline, BCVA 20/200 or worse.
- For participants who had worsening versus baseline on BCVA, the outcome on the last BCVA value will be displayed: Recovered to baseline, Not recovered to baseline, Lost to follow-up or dead with ongoing corneal events

A participant will be considered as lost to follow-up if the participant discontinued the study and did not perform any follow-up visit.

A shift table of the category of the last BCVA value (Normal (20/20 or better), worse than 20/20 up to 20/40, worse than 20/40 up to 20/200 or 20/200 or worse) versus the category of the worst BCVA value (20/40 or better, worse than 20/40 up to 20/200, 20/200 or worse) will be performed for participants who experienced at least one treatment-emergent corneal event.

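### In participants with several corneal events, the SAP's outcome ranking lets a recovered event hide one whose outcome is unknown

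*SAP*

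**What the plan says.** SAP 3.6.2 plans a per-participant summary of treatment-emergent corneal events. For the outcome line it states that "in case of multiple events with different outcomes, the most severe outcome will be tabulated", and gives an order, worst first, that runs from fatal through not recovered and recovering to "recovered or resolved with sequelae, recovered or resolved, unknown". The ranking therefore operates only when a participant has two or more corneal events and their outcomes differ.

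Two other planned outputs bear on recovery and do not use this order:

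- Time to recovery, also in SAP 3.6.2, is summarised among participants with at least one occurrence that resolved, with or without sequelae. It uses each participant's longest duration.
- The last best corrected visual acuity (BCVA) value, in SAP 3.6.3.2, is classified for participants whose acuity worsened, as "Recovered to baseline, Not recovered to baseline, Lost to follow-up or dead with ongoing corneal events".

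Protocol 2.3.1 names corneal toxicity as the main anticipated risk. Of the earlier clinical experience, its Table 1 says: "The corneal TEAEs were manageable and reversible".

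**The concern.** A worst-outcome rule should not give a participant a favourable label while one of that participant's events has no known resolution. Placing *unknown* last does this: it treats absence of information as a milder state than documented recovery.

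The neighbouring lines of the same corneal summary do not have this feature. For relationship, any related event makes the participant related. For action taken, the order runs from drug withdrawn to dose not changed and has no unknown category. Only the outcome line lets a missing value lose to the best value.

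At stake is the accuracy of one descriptive row that reports directly how corneal events ended, for the toxicity of most interest in this programme. Multiple events per participant are foreseen: SAP 3.6.2 defines recurrence and plans to analyse it, and Protocol 10.6 (Table 10) has entries for second episodes of keratopathy.

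**Working it through.** The documents give no figure that depends on this rule, so there is none to reproduce. The check has two parts: what the rule does, and how many participants it could touch.

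**1. The rule applied to each combination**

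There are six outcome categories. The sets of outcomes that a participant can have and that include *unknown* number 2^5 = 32. For a participant with *unknown* plus one other outcome, or *unknown* alone:

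| Outcomes present | Tabulated under SAP order | With *unknown* just above *recovered* |
|---|---|---|
| unknown only | unknown | unknown |
| recovered + unknown | **recovered** | **unknown** |
| with sequelae + unknown | with sequelae | with sequelae |
| recovering + unknown | recovering | recovering |
| not recovered + unknown | not recovered | not recovered |
| fatal + unknown | fatal | fatal |

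Moving *unknown* above k categories changes 2^k − 1 of the 32 sets, namely those in which every other outcome present is one of the k categories:

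- Above *recovered* only (k = 1): 2 − 1 = 1 set changes, recovered + unknown.
- Above both recovered categories (k = 2): 4 − 1 = 3 sets change. Two of these contain a known sequela, which would then be replaced by *unknown*.
- Above *recovering* as well (k = 3): 8 − 1 = 7 sets change, so that known *recovering* outcomes are overwritten too.

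**2. Scale**

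Inputs: 56 of 186 patients with corneal events at 100 mg/m² every 2 weeks in the first-in-human study (Protocol 2.3.1, Table 1), and about 38 treated participants planned (SAP 4).

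- Rate: 56/186 = 30.1%.
- Expected participants in the row: 0.301 × 38 = 11.4, about 11.
- Weight of one participant: 1/11 = 9.1%, about 9 percentage points.

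The documents give neither the share of these participants with more than one event nor the share of events with unknown outcome. As an illustration, assume that a share m has exactly two events, that each event independently has unknown outcome with probability u, and that all other events recovered. Then:

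- Expected number masked = 11 × m × 2u(1 − u).
- Low case, m = 0.20 and u = 0.05: 11 × 0.20 × 2 × 0.05 × 0.95 = 0.2.
- High case, m = 0.50 and u = 0.20: 11 × 0.50 × 2 × 0.20 × 0.80 = 1.8.

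Under the same assumptions, the expected number of single-event participants correctly left as *unknown* is 11 × (1 − m) × u. Over the same ranges this runs from 11 × 0.50 × 0.05 = 0.3 to 11 × 0.80 × 0.20 = 1.8.

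**The case against.** The case for leaving the text alone has five parts.

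- **Other outputs cover recovery.** Time to recovery, time to recurrence, and the BCVA outcome and shift tables do not use this ranking, and BCVA has its own category for loss to follow-up or death with ongoing events. This is true and limits the consequence. It does not close the gap. Time to recovery reports durations and has no category for unknown outcome. The BCVA outcome covers only participants whose acuity worsened, whereas Protocol 10.6 describes Grade 1 keratopathy as asymptomatic and seen only on examination.

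- **Follow-up should make unknown outcomes rare.** Protocol 8.2.2 and 8.2.6.2 call for repeated ocular examination until events settle, ocular tests are scheduled at end of treatment, and drug-related events are followed to resolution or stabilisation. This stands as a reason to expect small numbers. Unknown outcomes remain possible, for instance after withdrawal.

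- **The SAP has no general worst-case convention to breach.** A reader might infer one from the rule "If the assessment of the relationship to IMP is missing for an AE, this AE will be assumed as related to IMP", or from the default of incomplete onset dates to treatment-emergent. But the same section leaves a missing grade as missing and counts it only under all grades. The objection stands, and the point here rests only on the logic of a rule that claims to pick the most severe outcome.

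- **The order of the other categories is defensible.** A reader might see a second fault in *recovering* outranking *recovered with sequelae*. That order keeps a participant with an ongoing event out of both recovered categories, so it does not inflate recovery.

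- **Reversibility does not rest on this row.** The Protocol's statement describes earlier studies. That is correct, and no claim is made here that it depends on this table.

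**Conclusion.** The point holds as a minor correction to one descriptive safety row. A participant with at least one recovered corneal event, at least one of unknown outcome and nothing worse is tabulated as recovered, and the resulting error can only favour recovery.

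A reader might infer that any participant with an unknown corneal outcome is reported as recovered. The documents do not support that: the ranking applies only to multiple events with different outcomes, and of the 32 possible sets containing *unknown* just one is tabulated as plain recovered.

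The likely size is 0 to 2 participants out of about 11. That rests on the earlier 30.1% rate carrying over to this population and on assumed shares of multiple events and unknown outcomes, so no effect at all is within the range. The primary endpoint and the interim decision are untouched, as are time to recovery and the BCVA results.

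**What to change.** In the outcome line of the corneal event summary in SAP 3.6.2, move *unknown* so that it sits between *recovered or resolved with sequelae* and *recovered or resolved*. Only the recovered-plus-unknown case then changes, and no known worse outcome is hidden. Placing *unknown* any higher is not advised, because it would overwrite documented sequelae or ongoing recovery with no information.

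The cost is one line of SAP wording and the matching line of table programming, best done before corneal outcomes are tabulated. The downside is that the reported recovered share may be slightly lower.

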1.1 STUDY DESIGN

This is a single group, Phase 2, open-label, multi-center study assessing efficacy (anti-tumor activity), safety, and PK of tusamitamab ravtansine single agent in NSQ NSCLC participants with negative (ie, intensity 1+ whatever the percentage of stained tumor cells or <1% of tumor cells) or moderate (ie, intensity \geq 2+ in \geq 1% and <50% of tumor cells) CEACAM5 expression tumors and high circulating CEA (\geq 100 ng/mL) at baseline.

During the pre-screening phase, participants who were pre-screened failed in the EFC15858 Phase 3 trial with available CEACAM5 status (central assessment by immunohistochemistry, IHC) as negative or moderate expression on archival tumor tissue can be pre-screened for ACT17241 study. Participants with high circulating CEA (≥100 ng/mL) will be screened and will go through protocol screening procedures.

This study is designed to obtain preliminary efficacy, safety and PK data on tusamitamab ravtansine administered as monotherapy at 100 mg/m² Q2W to participants with NSQ NSCLC tumors with CEACAM5 moderate-negative tumor expression and high circulating CEA levels.

Approximately 285 participants will be pre-screened to achieve approximately 38 treated participants, based on an estimated pre-screening failure rate of 84% and an estimated study screening failure rate of 15%.

The cycle duration is 2 weeks. The median expected duration of study per participant is estimated as 40 weeks: up to 4 weeks for screening, a median of 24 weeks for treatment, and a median of 12 weeks for end of treatment assessments and the safety follow-up visit. Enrolled participants may receive study intervention until disease progression, unacceptable AE, initiation of a new anticancer therapy, or the participant's or Investigator's decision to stop the treatment, whichever comes first.

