3 STATISTICAL ANALYSES

3.1 GENERAL CONSIDERATIONS

This study is not intended to explicitly test a hypothesis. For the primary and secondary efficacy endpoints, 95% CIs will be provided.

All efficacy endpoints based on radiological assessments of tumor burden (ie, ORR, DOR, PFS, and DCR) will be derived using the local radiologist's/Investigator's assessment.

In general, continuous data will be summarized using the number of observations available, mean, standard deviation, median, Q1, Q3, minimum, and maximum. Categorical and ordinal data will be summarized using the count and percentage of participants.

The baseline value is defined as the last available value before the first dose of IMP.

The study cut-off for analysis of the primary endpoint, ORR, corresponds to the date on which all evaluable treated participants have had at least 2 postbaseline tumor assessments, experienced confirmed objective response, or have discontinued the study treatment for any reason. For participants with 2 postbaseline tumor assessments and occurrence of response at the second postbaseline tumor assessment, it will also include the confirmatory assessment. This study cut-off can be up to approximately 20 weeks (16 weeks for 2 tumor assessments and 4 weeks for confirmation of response, if needed) after the last participant's first IMP administration. Of note, DCR will also be assessed at this cut-off.

The final study cut-off for analysis of the secondary efficacy endpoints, which include DOR and PFS, will be 4 months after the cut-off date for the primary analysis. At that time, the primary analysis of ORR and DCR will also be updated.

Observation period

The observation period will be divided into 4 segments:

- The **pre-treatment period** is defined as the period up to first IMP administration.
 - The **pre-screening period** is defined as the period from the pre-screening informed consent to the day before the screening informed consent.
 - The **screening period** is defined as the period from the screening informed consent up to the first IMP administration.
- The **on-treatment period** (ie, treatment-emergent period) is defined as the period from the first IMP administration to 30 days after the last IMP administration.
- The **post-treatment period** is defined as the period from the end of the on-treatment period.

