In addition to the analyses of deaths included in Table 4, the number (%) of participants in the following categories will be provided:

• Deaths during the treatment-emergent and post-treatment periods by study period and main reason for death

- An overview of Grade 5 AEs will be provided with the following categories:
 - Grade 5 AE (TEAE and post-treatment).
 - Fatal TEAE (regardless of date of death/period).
 - Grade 5 TEAE with a fatal outcome during the treatment-emergent period,
 - Any Grade TEAE with a fatal outcome during the post-treatment period.
 - Post-treatment Grade 5 AE (excluding a TEAE that worsened to Grade 5 during the post-treatment period).

In addition, a listing of deaths in non-enrolled participants or enrolled but not treated participants will be provided on the prescreened population.

Analysis of adverse events of special interest (AESIs) and other AEs of interest

Adverse events of special interest (AESIs) and other AEs of interest will be selected for analyses as indicated in Table 6. Number (%) of participants experiencing at least one event will be provided, by SOC and PT if applicable. Tables will be sorted as indicated in Table 4.

AESIs and other AEs of interest	Selection	
AESIs		
Grade ≥3 keratopathy/keratitis	e-CRF AESI specific tick box on the AE page. It could include Grade ≥3 events with PTs from CMQ of corneal events	
Bundle branch blocks or any conduction defects.	e-CRF AESI specific tick box on the AE page. It could include events with PTs from SMQ "Conduction defects"	
Grade ≥3 liver enzyme increased (symptomatic or asymptomatic)	e-CRF AESI specific tick box on the AE page. It could include Grade ≥3 events with the following PTs: "Alanine aminotransferase increased", "Aspartate aminotransferase increased", "Transaminases increased", "Hepatic function abnormal", "Hepatic enzyme increased", "Liver function test increased", "Transaminases abnormal", "Hepatic enzyme abnormal", or "Liver function test abnormal"	
Symptomatic overdose (serious or nonserious) with IMP	e-CRF symptomatic overdose specific tick box on the Overdose page	
Pregnancy of a female participant entered in a study as well as pregnancy occurring in a female partner of a male participant entered in a study with IMP	eCRF specific tick box for adverse event linked to pregnancy on the Pregnancy page	
Other AEs of interest		

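### The Kaplan-Meier curve for first corneal event censors death and the end of the treatment-emergent period, so it lies above the proportion of treated participants affected and should be labelled and paired with a cumulative incidence curve

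*SAP*

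**What the plan says.** SAP 3.6.2, in the part on occurrence and recurrence of corneal events, states: "The time to first onset of corneal event will be described using Kaplan-Meier curves". Time runs from first dose to first occurrence. For a participant with no event, "it will be censored at the end date of the treatment-emergent period, analysis cut-off date or date of death, whichever occurs first". SAP 3.1 fixes the length of the treatment-emergent period: it "is defined as the period from the first IMP administration to 30 days after the last IMP administration". No cumulative incidence estimate is planned, and the curve carries no estimand or label.

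The proportion affected is reported separately. For adverse events of interest, which include corneal events, SAP 3.6.2 says: "Number (%) of participants experiencing at least one event will be provided". The overview of treatment-emergent events and the corneal summary by worst grade also give counts and percentages.

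Protocol 2.3.1 says that "the main anticipated risk to patients is corneal toxicity". Its Table 1 gives corneal events in "30.1% of patients (56/186) in the pool of patients" at the study dose and schedule in TED13751. SAP 1.1 expects "a median of 24 weeks for treatment".

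**The concern.** The three censoring reasons differ in kind. The analysis cut-off is administrative: the participant is still at risk and simply has not been followed further. Death removes all risk of a first event. The end of the treatment-emergent period removes, by definition, the chance of a treatment-emergent event.

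Kaplan-Meier treats all three alike, as if those who left would have gone on to have events at the rate of those who remained. One minus Kaplan-Meier (1-KM) is then never below the Aalen-Johansen cumulative incidence from the same data, and the gap grows as participants leave treatment.

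This is the only Kaplan-Meier display among the SAP's safety analyses, and it concerns the main anticipated risk. A reader who takes a height off its right-hand side as the share of participants affected would get a figure above the crude percentage in the same section. Nothing in the SAP would explain the difference.

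**Working it through.** **Inputs from the documents**
- Crude corneal incidence: 56/186 = 30.1% (Protocol 2.3.1, Table 1), which reproduces the printed figure. It is the only document figure available for calibration and comes from another study.
- Median treatment duration 24 weeks = 168 days; at 30.4375 days per month (SAP 5.4.1), 5.52 months.
- Treatment-emergent period runs 30 days past the last dose: L = 30/30.4375 = 0.986 months.
- About 38 treated participants (SAP 4).

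**Assumptions not in the documents**
- Constant corneal hazard λ.
- Exponential treatment duration, so after L the exit rate is μ = ln 2/5.52 = 0.1256 per month.
- 30.1% is the eventual crude incidence.

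**Calibration.** Eventual cumulative incidence = 1 − e^(−λL) × μ/(λ + μ). Setting this to 0.301 gives λ = 0.0461 per month (0.0106 per week). Check: e^(−0.0461 × 0.986) = 0.9556; 0.1256/0.1717 = 0.7315; 1 − 0.9556 × 0.7315 = 0.301.

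**Formulas**
- 1-KM at t: 1 − e^(−λt).
- Cumulative incidence at t (for t > L): 1 − e^(−λL) + e^(−λL) × [λ/(λ + μ)] × [1 − e^(−(λ + μ)(t − L))].

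**Base case**

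| Time | 1-KM | Cumulative incidence | Excess (points) |
|---|---|---|---|
| 6 months | 24.2% | 19.3% | 4.9 |
| 10 months | 36.9% | 24.6% | 12.3 |

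In this scenario 1-KM passes the eventual crude 30.1% at −ln(0.699)/0.0461 = 7.8 months. For scale, the binomial standard error with N = 38 is √(0.193 × 0.807/38) = 6.4 points at 6 months and √(0.246 × 0.754/38) = 7.0 points at 10 months.

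**Sensitivity (one assumption changed at a time)**

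| Change | 6 months | 10 months |
|---|---|---|
| All onset within 2 months | 0.8 | 0.8 |
| All onset within 3 months | 2.3 | 2.3 |
| All onset within 4 months | 3.9 | 3.9 |
| Falling onset hazard (Weibull shape 0.5) | 3.4 | 7.2 |
| Rising onset hazard (Weibull shape 1.5) | 5.1 | 15.5 |
| Median treatment 32 weeks | 3.1 | 8.3 |
| Median treatment 16 weeks | 8.7 | 19.9 |
| No 30-day extension | 7.9 | 16.7 |
| 30.1% reached by month 10, not eventually | 6.0 | 14.5 |
| Crude incidence 20% | 3.1 | 8.2 |
| Crude incidence 40% | 6.7 | 16.0 |

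The range is about 1 to 9 points at 6 months and about 1 to 20 at 10 months.

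**Death alone as the competing event.** Let deaths be an assumed share s of treatment exits, with hazard d = sμ from day 1. The excess is [1 − e^(−λt)] − [λ/(λ + d)] × [1 − e^(−(λ + d)t)].
- With λ = 0.0461 and s from 5% to 30%: 0.4 to 2.4 points at 6 months and 1.1 to 5.7 at 10 months.
- With λ = 0.0541, the value calibrated without the 30-day extension, and s = 30%: 2.7 points at 26 weeks and 6.4 at 10 months.

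Most of the base-case gap therefore comes from the end of the treatment-emergent period, not from death.

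**The case against.** The best defence is that censoring at the end of exposure plus 30 days answers a legitimate question: how quickly corneal events appear while a participant is being treated. For an exposure-driven toxicity that is a reasonable estimand. A corneal event after that window can still occur; it would be classed as post-treatment. Counting the end of treatment as a competing event answers a different question, and that curve ends near the crude percentage already tabulated. This part stands. It means the Kaplan-Meier curve is not wrong in itself. However, the on-treatment reading needs non-informative stopping, and the SAP states neither that assumption nor the reading, although it names a hypothetical strategy for PFS and DOR in 3.3.2.2.

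It also stands that the SAP plans no 6- or 10-month corneal probabilities, whereas it asks for landmark estimates for PFS and for time to symptom deterioration. A reader might infer that the trial will report corneal incidence from this curve, or that the report will carry two conflicting incidences. The documents do not support that: the proportion affected is tabulated as number (%), and the curve is a time-to-onset description.

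The calibration mixes sources. The 30.1% comes from a pool in another study whose treatment duration is not given, while the 24-week median is this trial's planning figure.

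Finally, the safety analysis is descriptive, and any misreading would overstate toxicity, not hide it.

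**Conclusion.** The point holds as a minor one. The direction is certain: 1-KM cannot be below the cumulative incidence, and it exceeds it once events follow earlier exits. The size is not fixed by the documents. A reader might take 5 points at 6 months and 12 at 10 months as the bias of this plan. Those figures belong to one scenario, with constant onset hazard, exponential treatment duration and a borrowed 30.1% as eventual incidence. If all onset falls in the first two months the excess is under 1 point at both times; with a 16-week median it is about 9 and 20. The part due to death, which does not depend on how one regards stopping treatment, is a few points and below the standard error with 38 participants. What is missing is a label saying what the curve estimates, and a companion curve for the proportion actually affected over time.

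**What to change.** In SAP 3.6.2, add an Aalen-Johansen cumulative incidence curve for first treatment-emergent corneal event. Treat death and the end of the treatment-emergent period as competing events, and censor only at the analysis cut-off for participants still in that period. At the interim and first-step analyses, SAP 3.8 closes the period at the cut-off for participants still on treatment; code that closure as administrative censoring, not as a competing event.

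If the Kaplan-Meier curve is kept, label it as onset conditional on remaining on treatment, state the non-informative stopping assumption, and do not read incidences from it.

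The existing censoring rule already needs every date involved, so no extra data are required. The cost is a few lines of SAP wording and one extra figure.
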